### **3.2 Dosing Rationale**

Although no serious adverse events are anticipated with the doses we propose, the first cohort of subjects will be a run-in of three patients receiving 50mg suppositories. If no mucosal or systemic adverse events are reported, we will proceed with 200mg dosing.

A five-day dosing regimen with a single dose of 200 mg per 24-hour period is selected based on the clinical toxicology and pharmacology database from anti-malarial and cancer trials as well as the performance data presented on the inhibition of HPV infected cells *in vitro* and *in vivo*. We anticipate that intra-vaginal administration of 200 mg Artesunate suppositories to the cervix will provide a local drug concentration well above IC50 of HPV-infected cells. Based on our experimental experience in nonclinical studies, we plan to assess more than one 5-day treatment cycle to explore potential dosing regimens suitable for subsequent phases of clinical studies.

The doses selected for this study are 50 mg and 200 mg. A dose level of 200 mg is equivalent to  $\leq 4\text{mg/kg}$  based on a minimum body weight of 50 kg as a subject inclusion criterion. The proposed dose level should be extremely safe as it is well within WHO recommended pre-referral dose for parenteral Artesunate treatment of severe malaria in young children; that is a single dose of 10mg/kg body weight. The proposed dosing regimen also resembles WHO recommended multi-day dosing regimen for adults and children with severe malaria upon hospitalization; that is 2.4mg/kg IV or IM TID on day 1 (or 7.2 mg/kg) and continued daily dosing at 2.4mg/kg for a total of 7 days [43]. Due to the rapid rate of elimination *in vivo*, negligible systemic accumulation of Artesunate or DHA metabolite is expected over multi-day dosing, especially in the case of local administration.

In summary, local intravaginal administration of Artesunate as a suppository at the highest dose in this study, 200 mg or approximately  $\leq 4\text{ mg/kg}$  is not expected to cause any systemic toxicity. Although no serious adverse events are anticipated with the proposed doses, dose escalation will only occur if no mucosal or systemic adverse events are reported in the first cohort of three subjects who receive the lowest dose. Subjects will be monitored for any unexpected adverse events locally and systemically.

## **4.0 OVERALL ASSESSMENT OF RISKS AND POTENTIAL BENEFITS**

### **4.1 Potential Risks**

The major risks for the study subjects are associated with surgical excision procedures that are the standard of care for patients with CIN2/3. Other potential risks posed by this clinical protocol would include local tissue irritation due to the presence of the investigational drug, and venipuncture for peripheral blood collection.

Intra-vaginal administration of Artesunate suppositories has not been approved for general use by the Food and Drug Administration (FDA). An Investigational New Drug (IND) application covering the proposed was submitted to the FDA. Approval to conduct this clinical trial was obtained from the FDA before clinical enrollment began. The IND governing this protocol is IND 124299. In parallel, the clinical trial protocol

was reviewed and approved by the Johns Hopkins Hospital Institutional Review Board, and the Johns Hopkins Cancer Center Clinical Research Committee.

#### **4.2 Known Potential Benefits**

This study is designed to assess safety, tolerability, and feasibility of using Artesunate suppositories in women with CIN2/3. Treated subjects whose CIN lesions regress during the study period would avoid the need for surgical LEEP or cone excisional biopsy procedure.

In summary, the potential to develop a non-invasive therapy for this disease is worth the minimal risk with this study.

#### **5.0 RATIONALE FOR CLINICAL TRIAL DESIGN**

This trial is a prospective, open, dose-escalation study of topical Artesunate, formulated as a suppository, administered intravaginally, prior to standard therapeutic resection of the squamocolumnar junction at study week 15. An initial dose cohort of 3 subjects will receive intravaginal Artesunate for one 5-day treatment cycle. Based on clinical experience with Artesunate, we expect that absorption in the cervical mucosa, which is stratified squamous epithelium, will be less than what is observed with rectal administration, which is a single layer of glandular epithelium. Because cervical stroma is much less vascularized than colorectal stroma, we also expect significantly lower systemic levels of Artesunate in subjects receiving intravaginal dosing. The goal of topical administration is to achieve local, mucosal distribution of study drug, as opposed to systemic levels.

If we do not observe untoward side effects, including mucosal excoriation, in the first dose cohort, we will proceed with dose-escalation. The subsequent cohort will undergo two cycles of treatment, spaced at 2-week intervals. The final cohort will undergo a total of three cycles of treatment, spaced at 2-week intervals. All subjects will undergo an interval colposcopic exam at study week 6. At week 15, if there is still a colposcopically detectable lesion, subjects will undergo standard therapeutic resection. If no lesion is obvious, a biopsy will be taken at the site of the original lesion. The cohort receiving the fewest cycles of Artesunate, and showing therapeutic effect will be expanded (see Section 12 for details). At each vaginal exam, cervical swabs will be obtained and cryopreserved. Peripheral blood will be obtained by venipuncture at baseline, and at study weeks 5, 15, and 28, 41, and the postop visit, and will be cryopreserved for assessment of biomarkers.

This clinical cohort, healthy subjects with colposcopically-directed, biopsy-confirmed CIN2/3, was selected for safety reasons. The study protocol window (15 weeks), is within the standard of care. In pregnant women who have a cervical HSIL, the standard of care is to follow colposcopically until postpartum [7]. We and others have reported that the probability that CIN2/3 will progress in this timeframe is essentially zero [63]. In fact,

we and others have also reported that in this timeframe, approximately 20-25% of CIN2/3 lesions associated with HPV16 will undergo regression [63]. Lesions that are associated with HPV genotypes other than HPV16 are even more likely to regress in this timeframe [64]. Moreover, in this population, it is feasible to visualize directly, quantitate serially, and perform therapeutic resection of premalignant lesions. Based on safety and tolerability data in pediatric populations receiving intrarectal suppositories at a dose that is approximately five-fold compared to the regimen we propose in this clinical protocol, we do not expect dose-limiting toxicities with the dosage and regimen proposed in this proof-of-principle study. The [name] group has a decade of experience in the design and execution of prospective clinical protocols specific for this patient cohort, testing immunotherapeutic interventions prior to standard therapeutic resection of any residual lesions. [65, 66]. The parallel design of this trial will allow comparison of tissue-based endpoints in this cohort.

Despite the experience with active immunotherapy in other tumor models, it is still not clear what measures of immune response are relevant to lesion regression. In particular, it does not appear that classic measures of immune response, measured in the circulation, correlate at all with clinical response. Because the biology of HPV disease is extensively characterized; because there are known, quantifiable risk factors for persistence and progression of disease; because we have ready access to an immunocompetent population of patients at elevated risk for carcinoma development; and because we can directly visualize and subsequently therapeutically resect and analyze affected tissue; we are presented with an opportunity to rapidly evaluate therapeutic regimens, characterize relevant immune responses, and provide direction for future interventions, both in this disease and in other tumor models. The relatively long precursor phase in HPV disease also provides many opportunities for intervention, including, optimally, prophylaxis against the development of cancer.

A larger goal of these clinical trials is to correlate measures of immune response with known clinical parameters of disease. The larger implications of this effort lie in the identification of appropriate and relevant measures of the mucosal immune microenvironment. The identification of intermediate biomarkers in the tissue not only serves to further our understanding of the immune response and our efforts to manipulate it, but also has practical implications in the setting of monitoring patients at risk for disease recurrence or progression. In the case of high grade cervical intraepithelial neoplasia, lesion size and viral load are both quantifiable risk factors for persistent and progressive HPV disease. Therefore in these trials we will quantitate both outcome measures sequentially and correlate them with local tissue and peripheral measures of immune response.

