**Objectives**

Primary Objective:

- To determine and evaluate the safety, tolerability, and feasibility of intra-vaginal administration of Artesunate, administered via vaginal suppository, in healthy women with cervical intraepithelial neoplasia (CIN2/3)

Secondary and Exploratory Objectives:

- To measure the effect of intra-vaginal topical Artesunate administration on histology, based on the regression of CIN2/3 at study week 15, assessed as either CIN1 or no CIN lesion detected by colposcopy/biopsy and cytology.
- To evaluate clearance of HPV as assessed by Hybrid Capture 2 DNA testing of cytologic specimens
- To evaluate the local tissue immune response
- To correlate measures of immune response with clinical response

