**Table 3: Outline of Evaluation Procedures**

	-3wks	Wk 0	Wk 2 	Wk 4 	Wk 6	Wk 15	Postop **	Wk 28	Wk 41
Informed consent	X								
Artesunate dosing		X	X	X					
Vital signs	X	X	X	X	X	X	X	X	X
Cervix check			X	X	X	X			
Medical history	X								
History of disease	X								
Demographic data	X								
Diary cards (give to pt)		X	X	X		X			
Diary cards (collect from pt)			X	X		X			
Adverse events		X	X	X	X	X	X	X	X
Inclusion/exclusion criteria	X								
Colposcopy	X				X	X		X	(X)*
Pap smear	X				X	X		X	X
HPV genotyping	X				X	X		X	X
Cervical swabs	X	X	X	X	X	X	X	X	X
LEEP/Cone**						(x)		(x)	
HLA testing ***	X								
PBL for banking****	X	(X)			X	X	X	X	X
Urine HCG	X	X	X	X		X			
Optional pheresis*****									

1. Treatment Group III

2. Treatment Group IV

\* Colposcopy only if clinically-required at wk 41

\*\* if residual disease is present (the procedure can happen any time after week 15, based on the physician's clinical judgment). The Postoperative visit will take place 4 +/- 1 weeks after the LEEP/Cone procedure.

\*\*\* HLA can be done at any time during the study, not an eligibility criterion

\*\*\*\* First blood draw can be done at either the screening visit or Wk 0, prior to dosing

\*\*\*\*\* pheresis is optional and can happen any time after week 15

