### **LEEP/Cone Excisional Biopsy Procedure**

After week 15, if there is residual colposcopic disease, the affected area will be excised using standard LEEP or cold knife cone technique. The resection specimens will be taken fresh to surgical pathology. Frozen section will be performed to confirm the presence or absence of CIN2/3. The frozen section block will be banked at  $-70^{\circ}\text{C}$ , and a sliver of tissue immediately facing the frozen section will be reserved for isolation of immune cells. This will allow unhampered routine diagnostic ability as well as preserve tissue sections frozen for characterization of inflammatory cell infiltrates. Routinely processed formalin-fixed, paraffin-embedded sections will also be analyzed for the characterization and quantitation of tissue infiltrates.

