### 12.4 Additional exploratory analysis

In addition to hypothesis testing, we will characterize the change in HPV viral load over the course of the trial using longitudinal data modeling. For each individual, we will have data on HPV viral load at weeks -2 (Screening visit), 9-10, and 15. A random effects model will be used to model the distribution of HPV viral load over time:

$$hpv_{it} = \beta_{0i} + \beta_1 t + \beta_2 t^2 + \varepsilon_{it}$$

where  $hpv_{it}$  is individual  $i$ 's HPV viral load at week  $t$ . Correlations between observations within an individual are accounted for by the random intercept (i.e. random effect) term. A quadratic model is used to account for non-linearity in the change of HPV viral load. From the fitted model, we can estimate the effect of the vaccine treatment on viral load. The plot below is based on simulated data and shows the type of result we hypothesize: a downward trend in HPV viral load that flattens as time increases. Based on the random effects model shown above, we can estimate the average response (denoted by the thick line) and better understand the association between the vaccine and response and specifically when changes in viral load tend to occur.

Lesion size will also be described using the random effects linear longitudinal model described above to look for time trends.

The secondary efficacy endpoints will be compared with analogous data obtained in a currently open cohort study, “Evaluation of Tissue and Peripheral Blood Immune Response in Women with HPV16+ Cervical Intraepithelial Lesions” (Johns Hopkins IRB# NA\_00037578). This observational cohort protocol has been open since 1999, and currently includes over 250 subjects. These subjects have the same eligibility criteria as the criteria for this trial, and are followed prospectively for the same timeframe, before undergoing standard therapeutic resection at week 15. To date, no CIN2/3 lesions have progressed to invasive disease in this timeframe, which is well within the standard of care. We will compare changes in HPV viral load and lesion size from baseline at Week 15, rates of histologic regression, and change in viral load over the 15 week window, in both cohorts.

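### The week-15 regression comparison in Section 12.4 may set biopsy-scored women against resected women, and conflicting scoring rules leave both the direction and the size of the bias open

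*Combined protocol and SAP*

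**What the plan says.** **Trial, week 15.** Resection is conditional. Section 5.0: "At week 15, if there is still a colposcopically detectable lesion, subjects will undergo standard therapeutic resection". For the other women: "If no lesion is obvious, a biopsy will be taken at the site of the original lesion". The footnote to Table 3 makes LEEP/cone conditional too: "if residual disease is present (the procedure can happen any time after week 15, based on the physician's clinical judgment". Section 10.4 agrees: "After week 15, if there is residual colposcopic disease, the affected area will be excised using standard LEEP or cold knife cone technique". Section 10.3 ties excision to residual abnormal tissue at weeks 15 and 28. Section 4.2 presents avoided surgery as a benefit: "Treated subjects whose CIN lesions regress during the study period would avoid the need for surgical LEEP or cone excisional biopsy procedure".

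**Comparison cohort.** Section 12.4 says that its members "are followed prospectively for the same timeframe, before undergoing standard therapeutic resection at week 15", and states no exception.

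**Comparison.** Section 12.4 will compare, among other things, "rates of histologic regression, and change in viral load over the 15 week window, in both cohorts".

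**Scoring.** There are two incompatible rules.
- The Synopsis objective takes regression as "assessed as either CIN1 or no CIN lesion detected by colposcopy/biopsy and cytology".
- Section 7.2 classes regression as none or total according to whether the tissue excised at week 15 contains CIN2/3. Section 12.2 likewise sets the entry biopsy against the exit cone.

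No section discusses biopsy false negatives or a difference in ascertainment between the two groups.

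**The concern.** A biopsy at one site can show that CIN2/3 is present, but it cannot exclude CIN2/3 elsewhere as well as an excised specimen can. If one group's regression rate rests partly on biopsies and the other's wholly on resections, the rates can differ with no drug effect. The trial is open-label, and the colposcopic judgement at week 15 decides which specimen a woman contributes.

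At stake is the reading of histologic regression against natural course. The group most affected is the women whose lesions seem to have gone. These are the likeliest treatment successes, and they are the women for whom the plan has no settled score.

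**Working it through.** The plan gives no power, expected difference or error rate for this comparison, so there is no stated figure to reproduce.

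**1. A trial woman with no visible lesion and a negative site biopsy**

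| Rule | Her score | Effect on treated rate if CIN2/3 was missed or she is omitted |
|---|---|---|
| Synopsis | Regressed, if cytology agrees | Up |
| Sections 7.2 and 12.2 | None, as there is no excised tissue | Down |

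**2. Size under the Synopsis rule, inert drug, cohort fully resected**

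Inputs:
- r, true regression: 0.20-0.25 (Section 5.0, given for HPV16-associated lesions).
- v, share of persistent CIN2/3 with no visible lesion at week 15: 0.10-0.30 (assumed).
- m, share of those missed by the site biopsy: 0.20-0.50 (assumed).

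Apparent rate = r + (1 − r) × v × m, so the excess is (1 − r) × v × m.
- Low corner: 0.75 × 0.10 × 0.20 = 0.015, or 1.5 points.
- High corner: 0.80 × 0.30 × 0.50 = 0.12, or 12 points. This is 12/20 = 60% of a 20% natural rate.

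In 30 women that is 30 × 0.015 = 0.45 to 30 × 0.12 = 3.6 extra women scored as regressed.

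Cytology is not in this formula. If it also missed a share c of the lesions that biopsy missed, the excess is multiplied by c. With c = 0.5, purely as an illustration, the range becomes 0.75 to 6 points.

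**3. Effect on a test**

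Section 12.4 names no test for this comparison. As an assumption, take the chi-square at p < 0.1 from Section 7.2, uncorrected, with 30 treated women against 250 in the cohort. Exact enumeration of the two binomials gives the chance of p < 0.1 in favour of an inert drug:

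| v, m | r = 0.25: apparent rate, chance | r = 0.20: apparent rate, chance |
|---|---|---|
| No bias | 25.0%, 5.5% | 20.0%, 5.5% |
| 0.1, 0.2 | 26.5%, 7.8% | 21.6%, 8.4% |
| 0.2, 0.4 | 31.0%, 18.7% | 26.4%, 21.7% |
| 0.3, 0.4 | 34.0%, 29.0% | 29.6%, 34.2% |

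**4. Size under Sections 7.2 and 12.2, biopsy-only women left out**

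Let s be the share of true regressors who still look abnormal and are resected (assumed 0-0.4). Apparent rate = r × s / [r × s + (1 − r)(1 − v)].
- s = 0: the rate is 0.
- r = 0.25, s = 0.4, v = 0.1: 0.10 / (0.10 + 0.675) = 12.9%.
- r = 0.25, s = 0.4, v = 0.3: 0.10 / (0.10 + 0.525) = 16.0%.

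Each is well below the true 25%.

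**5. Equal ascertainment**

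If the cohort followed the same conditional procedure and scoring rule, with the same v and m, both rates shift equally and the excess difference is 0.

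**The case against.** Several points on the other side stand.

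- **Direction.** A reader might infer that missed CIN2/3 is always counted as extra regression. That holds only under the Synopsis rule. Under Sections 7.2 and 12.2 the bias can run the other way.
- **Cohort procedure.** A reader might infer that every cohort woman was resected and that hidden disease was therefore found. This rests on one clause. Section 5.0 opens by describing the trial in the same short way, as treatment ahead of resection at week 15, and then makes resection conditional. Section 8.0 says that the trial's serial assessments parallel those of the cohort. The cohort may have followed the same rule.
- **Cytology.** The Synopsis rule requires it, and Table 3 schedules a Pap smear at week 15. A missed lesion must escape both tests, which points to the lower part of the range.
- **Reach.** This is not the only comparison with untreated women. Section 7.2 names the colposcopy database, whose ascertainment is not described. Section 12.4 also compares viral load and lesion size, which need no excised tissue.
- **Weight.** The trial is Phase I with safety as its primary outcome, and this comparison is exploratory. The expansion regimen in Section 12.1 is chosen on within-subject viral load and lesion clearance, not against the cohort.

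None of this supplies the missing scoring rule or says how cohort women without a visible lesion were assessed.

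**Conclusion.** The concern holds in a limited form. As written, the regression comparison can be biased by unequal ascertainment, and the plan neither prevents this nor would reveal it. The direction depends on which of two conflicting scoring rules is used: upward under the Synopsis rule, downward if biopsy-only women are dropped under Sections 7.2 and 12.2.

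The upward figure of about 1.5 to 12 points, before cytology, assumes a fully resected cohort, equally sensitive histology on all excised tissue, and values of v and m that are not in the documents. The natural rate used is for HPV16-associated lesions. Section 5.0 says that other types regress more often, which would shrink the persistent share and with it the excess.

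The documents do not support saying that efficacy will be overstated, or that the cohort was certainly examined more thoroughly. The matter should be put right before the comparison is run, but it does not touch the primary safety objective.

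**What to change.** 1. Reconcile the Synopsis objective with Sections 7.2 and 12.2 in one definition of histologic regression that states the score for a woman with a biopsy and no excised tissue.
2. State in Section 12.4 how cohort women without a visible lesion were assessed at week 15, and apply the same rule to both groups.
3. Report, for each group, how many women were scored on biopsy and how many on resection.
4. Present the comparison twice, with biopsy-negative unresected women counted (a) as regressed and (b) as unconfirmed, that is, not regressed. Describe any efficacy signal in the light of both results.
5. Show the trial's scheduled week-28 colposcopy, cytology and HPV results for these women as supportive data only. The documents describe no week-28 data for the cohort, and cytology and HPV tests give no histologic grade.

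The cost is revised wording, a check of the cohort's records and a few tabulations, with no new procedure and no change in management. Bound (b) is conservative, because it counts true regressors who were spared resection as failures, so the reported efficacy may look less favourable.

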## **6.0 STUDY OBJECTIVES**

This trial is designed to test the hypothesis that intra-vaginal application of Artesunate is well-tolerated in women with CIN2/3.

The primary objective is to evaluate the safety and tolerability of the intra-vaginal administration of Artesunate in study subjects.

The secondary objective is to explore clinical activity, such as clearance of HPV disease, corresponding to intra-vaginal administration of Artesunate.

## **7.0 STUDY OUTCOME MEASURES**

### **7.1 Primary Outcome Measures**

Safety will be assessed by the findings of adverse events, including dose related limiting AEs. Subjects will be monitored for the appearance of erythema, itching, burning, pain, infection, desquamation, tenesmus, bleeding, dizziness, and any unexpected AEs.

### **7.2 Secondary Outcome Measures**

Indicators of drug efficacy (see below) will be drawn from any evidence demonstrating a significant difference (by simple chi-square analysis;  $p < 0.1$ ) between treated subjects and the baseline data in the Johns Hopkins Colposcopy database

- Extent of lesion clearance (by lesion number, size, and/or area of coverage)
- Presence/absence of HPV DNA
- Regression of CIN stage by histopathology (comparison of initial biopsy to LEEP/cone excision-procured tissue).

Histologic regression will be judged as none (persistent CIN2/3 in week 15 resection specimen) or total (no CIN2/3 in resection specimen).

Virologic HPV viral load. Longitudinally obtained cervical swabs will be used to quantitate HPV viral load as a continuous variable.

Tissue sections from the diagnostic biopsy obtained as part of the screening process, and from the resection specimen obtained post-treatment will be assessed for expression of CD8 (effector T cells), CD71 (transferrin receptor), and cleaved caspase 3 (apoptotic cell death).

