## **8.0 STUDY DESIGN**

Prior to enrollment, patients referred for evaluation of an HSIL pap smear will undergo a full colposcopic evaluation, with biopsy confirmation. Clinical, histopathologic, virologic, and immunologic parameters will be assessed longitudinally in each study participant, as outlined below. The trial is a dose-escalation design, with a run-in cohort to assess the likelihood of mucosal irritation.

These serial assessments will directly parallel those obtained in the currently open CIN2/3 cohort study (JHMI JCCI# 99-08-27-04). Those patients who have measurable disease after biopsy will be eligible for study participation.

Cervical tissue specimens obtained as routine diagnostic and therapeutic specimens will be analyzed to characterize local tissue immune response. Diagnostic biopsies obtained at initial colposcopy will be used to confirm the diagnosis of CIN2/3. The initial diagnostic biopsy specimens will also be characterized in terms of type and quantitation of inflammatory cell infiltrates. Immunocytochemical techniques will be used to determine presence and numbers of macrophages, dendritic cells, T cells, B cells, and NK cells. We will also use standard staining techniques to detect cleaved caspase 3. As tissue availability permits, the specimens will also be analyzed for other immune cells. We will be comparing tissue profiles with those obtained on circulating PBLs in our study population. In the post-suppository administration, therapeutic LEEP/cone biopsy specimens, markers of local tissue immune response will be similarly characterized and quantitated. [name] will review all of the histologic slides.

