## **9.0 STUDY POPULATION AND ENROLLMENT**

Patients with high-grade cervical intraepithelial lesions (CIN2/3) will participate in this study. At Johns Hopkins, patients will be recruited from the Johns Hopkins Colposcopy Service, and from referring physicians. Annually, the Colposcopy Service treats over 800 patients, approximately 15% of whom have high-grade lesions. In terms of feasibility, over the past 12 years we have recruited nearly 500 patients for screening to our cohort and vaccine studies, which consists of the same study population as the one described for this interventional trial. Of the HSIL patients approached for study entry, 80% have consented for screening. Of the patients who consented for screening, 33% were African American. This percentage is representative of our colposcopy population. It is anticipated that as therapeutic options become available through the upcoming Phase I trial, that referral volume will continue to increase.

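### Sections 7.2 and 12.4 name different external comparators for overlapping efficacy endpoints, and the one carrying the p<0.1 test has no stated untreated 15-week outcome

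*Combined protocol and SAP*

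**What the plan says.** Section 7.2 opens its list of secondary outcomes with a rule: "Indicators of drug efficacy (see below) will be drawn from any evidence demonstrating a significant difference". The test is a simple chi-square at p<0.1, and the contrast is "between treated subjects and the baseline data in the Johns Hopkins Colposcopy database". The rule covers extent of lesion clearance, presence of HPV DNA, and regression of CIN on histology. The protocol does not say what the database holds, how many women it would contribute, or at what time point.

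Section 12.4 describes another source: "The secondary efficacy endpoints will be compared with analogous data obtained in a currently open cohort study". That cohort "currently includes over 250 subjects", who are followed over the same window "before undergoing standard therapeutic resection at week 15". The planned contrasts are explicit: "We will compare changes in HPV viral load and lesion size from baseline at Week 15, rates of histologic regression". No test or threshold is given for them.

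Section 8.0 also refers to a cohort: "These serial assessments will directly parallel those obtained in the currently open CIN2/3 cohort study". It gives the identifier JHMI JCCI# 99-08-27-04, whereas Section 12.4 gives IRB# NA_00037578.

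On the natural course, Section 5.0 puts regression in this timeframe at about 20-25% for HPV16-associated CIN2/3, and says that lesions of other types regress more often. Section 9.1 admits any HPV-positive woman. The title of the Section 12.4 cohort restricts it to HPV16+ lesions, although that section describes the eligibility criteria as the same.

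**The concern.** Two of the three outcomes in Section 7.2, clearance and regression, are changes since entry. A drug effect on them shows only against women who were followed over the same interval without the drug. Section 12.4 has such women, but the p<0.1 rule is attached to something else. An analyst following Section 7.2 must guess what the database baseline means, and on the literal guess the test detects natural regression.

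What is at stake is modest but real. The Synopsis carries exploratory inferences at p≤0.10 forward for further study in later trials. A signal that an inert suppository would usually produce could misdirect that choice.

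**Working it through.** The plan states no sample size, power or effect size for either external comparison, so there is no figure to reproduce. The check asks how the Section 7.2 test behaves when the drug does nothing.

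**Inputs**
- Natural 15-week regression: 20-25% (Section 5.0, HPV16 lesions).
- Treated women: 9 per 200 mg cohort, 27 at 200 mg in all (Table 4).
- Threshold: p<0.1, simple chi-square (Section 7.2).
- Reference size: not stated. Assumed 120 (one year of high-grade patients, 15% of 800, Section 9.0) to 250 (the cohort size in Section 12.4).

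**Literal reading: comparator is status at entry, so 0 regressions**

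One regressor among 9 treated women already meets the threshold:
- 1/9 against 0/250: χ² = 259 × 250² / (9 × 250 × 1 × 258) = 27.9, p = 1.3 × 10⁻⁷; with Yates correction p = 0.011.
- 1/9 against 0/120: χ² = 129 × 120² / (9 × 120 × 1 × 128) = 13.4, p = 0.00025; with Yates correction p = 0.090.

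The chance that an inert drug is flagged is therefore the chance of at least one regressor:
- 9 women: 1 − 0.80⁹ = 86.6%; 1 − 0.75⁹ = 92.5%.
- 27 women: 1 − 0.80²⁷ = 99.8%; 1 − 0.75²⁷ is above 99.9%. With Yates correction two regressors are needed, giving 98.1-99.6%.

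The result depends on the reference size. With only 9 reference records against 9 treated women, three regressors are needed and the rate falls to 26-40% (9-17% with Yates). With 27 against 27 it is 93-98% (65-84% with Yates).

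**Cohort reading: comparator is week-15 outcome, n = 250**

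With the same true rate of 20-25% in both groups, exact enumeration for 27 treated women gives 9.8-10.0% rejections in total, of which 5.4-5.8% favour the drug. The test then behaves as intended.

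**Same data, opposite conclusions**
- 1 of 27 against 0/250: p = 0.0023.
- Against 56/250 (22.4%), 10 of 27 are needed: χ² = 277 × (10 × 194 − 17 × 56)² / (27 × 250 × 66 × 211) = 2.88, p = 0.090.

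Anything from 1 to 9 regressors among 27 is thus significant in favour of the drug under one comparator and not under the other.

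**HPV type**

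Suppose the cohort is HPV16-only at 22.5%, and natural regression in the mixed-type trial is 30-40% (an assumption; the protocol says only that it is higher). An inert drug is then flagged in 23-62% of trials with 27 treated women. Changing the comparator without handling HPV type leaves a large part of the problem.

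**The case against.** The strongest reply is that Section 7.2 is loosely worded and means a historical background rate. Its histology item compares the initial biopsy with excised tissue, which needs two time points, so a presentation-only record has no regression outcome to tabulate. Section 5.0 anticipates comparing tissue endpoints across parallel protocols, Section 8.0 aligns the assessments with the cohort, and Section 9.0 says that the group's earlier studies drew on the same population. On this view Section 12.4 already plans the right comparison. This reading is plausible and cannot be excluded. It does not remove the point, because the text neither equates the two sources nor attaches the test to the cohort, and it leads to the same edit.

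A reader might infer several stronger claims that the documents do not support:
- **That the database contains no 15-week outcome.** Its content is never described. Only the silence of Section 7.2 can be stated.
- **That the contrast is driven by clinic case mix.** Section 9.0 does say "Annually, the Colposcopy Service treats over 800 patients, approximately 15% of whom have high-grade lesions", but that is annual caseload and not the comparison set. Regression of CIN2/3 can be scored only in women who had it.
- **That the test decides efficacy for the trial.** The Synopsis has its own p≤0.10 rule, and Section 12.1 chooses the expansion dose on within-subject viral-load decrease and lesion clearance, with a fallback to overall safety and efficacy.
- **That both sections cover identical endpoints.** HPV DNA presence is listed only in Section 7.2, and viral load is what Section 12.4 compares.

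It is also fair that this is a phase I safety trial with mainly descriptive analysis, which limits the severity.

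**Conclusion.** The concern holds as a conflict between two sections over the external comparator, with the only chi-square comparison rule attached to the less defined source. The 87-92% figure applies to a nine-woman cohort and rests on three conditions: baseline means status at entry, the reference has 120 to 250 women, and natural regression is 20-25%. At 30%, which a mixed-type population could reach, it is 96%. Under the background-rate reading the excess disappears apart from the HPV-type mismatch, and what remains is an undefined term.

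The two cohort identifiers may denote one study registered in two systems; the protocol does not say.

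The effect is confined to exploratory secondary efficacy signals. Neither the safety conclusions nor the expansion-dose rule depends on this test. It should be corrected, but it does not threaten the trial's primary purpose.

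**What to change.** In Section 7.2, replace the database baseline with the week-15 outcomes, as change from entry, of the Section 12.4 cohort. In both sections:
- Name that cohort as the external comparator under one identifier, reconciling Sections 8.0 and 12.4.
- Apply this trial's entry criteria and outcome definitions to the cohort women.
- Exclude from the comparator any woman treated in this trial, since the cohort is still open.
- Attach the chi-square test at p<0.1 to this comparison for the binary outcomes.
- Restrict the comparison to HPV16+ treated women, or stratify by HPV type where the cohort allows, and report non-HPV16 women descriptively.
- For HPV DNA presence, say whether the cohort has it at week 15; if not, report it without a test.

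The change is to text and analysis only, using data already planned for use. The cost is a lower chance of a nominally positive signal and fewer treated women in the HPV16 comparison. Against 22.5% in 250 cohort women, power in favour of the drug is 62% at a true regression rate of 40% and 90% at 50% with 27 treated women. With 9 it is 35% and 58%. The protocol does not give the HPV16 share of the trial, so the realised figure may lie between these.
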